be summarized. Estimates of the ccRCC ORR along with the associated 90% and 95% exact binomial confidence intervals (Clopper-Pearson method) will be provided. The binomial probability that the observed ccRCC ORR is > 0.15 will be calculated. Best confirmed response will be summarized. The ccRCC TTR will be calculated for patients who achieve a ccRCC CR or PR. The maximum percent decrease in ccRCC tumor burden will be displayed using waterfall plots. The ccRCC PFS and ccRCC DOR will be summarized descriptively using the Kaplan-Meier method. The median and quartiles of ccRCC PFS and ccRCC DOR will be calculated along with 90% and 95% confidence intervals.

Summaries of the response endpoints will also be provided for subgroups of the Efficacy Analysis Set as follows: Subgroups will be defined based on site of primary tumors other than ccRCC at screening, blood level of PT2385 based on the PK assessments, and duration of PT2385 treatment. The analyses of ORR, PFS, best confirmed response, and DOR will be performed in each of these subgroups.

The ORR, PFS, DOR, and TTR will be summarized for the individual types of non-ccRCC tumors using modified RECIST 1.1 criteria. The modification to RECIST 1.1 is to evaluate different organ system tumors independently (e.g., VHL disease-associated solid tumors in the pancreas, adrenal gland, or hemangioblastomas or retinal angiomas).

The determination of response and progression will be made by the local investigators. The investigator assessments will be used for decisions regarding treatment for individual patients and by the DMC for approval to open Stage 2 of the study. The response outcomes will also be reviewed and determined by an Independent Review Committee (IRC). For the primary analysis of ORR, the determination of response will be based on independent radiologic assessment conducted by the IRC. Both the investigators' and the IRC's assessments will be used for the summaries and analyses of efficacy.

Safety Assessments

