11. PHARMACOKINETIC ASSESSMENTS

Blood samples for the determination of plasma concentrations of PT2385 and its primary metabolite PT2639 will be collected at the Week 1, Day 1 visit before and 6 hours after study drug administration and at the Week 3, Week 5 and every 4 weeks through the Week 17 visits before study drug administration (Schedule of Events, Appendix 1). The date and time of collection of all PK blood samples should be recorded.

Validated liquid chromatography/mass spectrometry methods will be used to assay the samples for plasma concentrations of PT2385 and PT2639. Additional metabolites, if detected, may be assessed using non-validated methods. Details for the collection, processing, storage, and shipment of samples can be found in the study laboratory manual.

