The ccRCC DOR will be calculated for patients who achieve a ccRCC CR or PR. For such patients, the ccRCC DOR is defined as the interval from first documentation of response, as determined by RECIST 1.1, to the earlier of the first documentation of disease progression or death from any cause. Dates of progression and censoring will be determined as described for the analysis of ccRCC PFS. Kaplan-Meier methods will be used to estimate the distribution of ccRCC DOR. Quartiles including the median will be estimated by KM method along with their 95% confidence intervals. KM cumulative estimators along with the associated 95% CIs will be provided for ccRCC DOR rates at 26, 39 and 52 weeks. These estimates will be used as estimates of durable response.

The ccRCC TTR will be calculated for patients who achieve a ccRCC CR or PR. Renal cell carcinoma TTR is defined as the interval from the start of study treatment to the first documentation of a ccRCC response of PR or better, as determined by RECIST 1.1.

The maximum percent decrease in ccRCC total tumor burden will be displayed using waterfall plots.

Summaries of the response endpoints will also be provided for subgroups of the Efficacy Analysis Set as follows: Subgroups will be defined according to blood level of PT2385 based on the PK assessments and duration of PT2385 treatment. The analyses of ccRCC ORR, ccRCC PFS, ccRCC best confirmed response, ccRCC DOR, and ccRCC TTR will be performed in each of these subgroups.

The ORR, PFS, best confirmed response, DOR, and TTR will be summarized for the nonccRCC tumors associated with VHL disease based on the subgroups of patients in the Efficacy Analysis Set who have the particular type of tumor. The determination of best response and date of progression will be determined by modifying RECIST 1.1 criteria to assess tumors in individual organ systems independently (e.g., VHL disease-associated solid tumors in the pancreas or adrenal gland, or hemangioblastomas or retinal angiomas).

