13.3.5. Pharmacodynamic Analyses

Blood samples for assessment of pharmacodynamic parameters such as EPO will be obtained in conjunction with PK samples, before (pre-dose) and 6 hours after study drug administration at the Week 1 visit and only before study drug administration at the Week 3 and 5 visits.

The value, change from baseline, and percent change from baseline will be listed and summarized for each scheduled time-point during the study for each of the pharmacodynamic parameters.

To investigate the effect of these potential biomarkers on efficacy, the association of baseline pharmacodynamic parameters with ORR and PFS will be investigated using exploratory multivariate techniques, subgroup analyses, and regression modeling.

The summaries will be based on the Safety Analysis Set. The exploratory analyses will be performed for the Efficacy Analysis Set.

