13.3.7. Pharmacokinetic Analyses

Blood samples for calculation of concentration of PT2385 and PT2639 will be obtained before (pre-dose) and 6 hours after study drug administration at the Week 1 visit and only before study drug administration at the Week 3, Week 5, and every 4 weeks through the Week 17 visits. The blood concentrations of PT2385 and PT2639 at each collection time will be summarized. Figures displaying individual and mean blood concentrations will be provided.

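### PT2385 exposure is related to efficacy only through descriptive blood-level subgroups with unstated cuts, although concentration and percent tumor change are both continuous and already collected

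*Combined protocol and SAP*

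**What the plan says.** Section 13.3.4 (Efficacy Analyses) provides for summaries of the response endpoints in subgroups: "Subgroups will be defined according to blood level of PT2385 based on the PK assessments and duration of PT2385 treatment". It continues: "The analyses of ccRCC ORR, ccRCC PFS, ccRCC best confirmed response, ccRCC DOR, and ccRCC TTR will be performed in each of these subgroups". The synopsis has a parallel sentence, "Subgroups will be defined based on site of primary tumors other than ccRCC at screening, blood level of PT2385 based on the PK assessments", and lists ORR, PFS, best confirmed response and DOR but not TTR. Neither place gives the number of groups, the cut points, or the rule that turns several samples into one blood level.

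Both underlying quantities are continuous. Section 11 states: "Validated liquid chromatography/mass spectrometry methods will be used to assay the samples for plasma concentrations of PT2385 and PT2639". Samples are taken before and 6 hours after the dose at Week 1, then pre-dose at Weeks 3, 5, 9, 13 and 17 (Section 11; Appendix 1, note 12). On tumor size, Section 13.3.4 says: "The maximum percent decrease in ccRCC total tumor burden will be displayed using waterfall plots". That plot is the only use made of percent change.

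Elsewhere the concentrations are described but not related to outcome. Section 13.3.7 says "The blood concentrations of PT2385 and PT2639 at each collection time will be summarized" and adds figures of individual and mean values. Regression is planned in Section 13.3.5, but for other predictors: "the association of baseline pharmacodynamic parameters with ORR and PFS will be investigated using exploratory multivariate techniques, subgroup analyses, and regression modeling". Section 13.3 states that there will be no inferential analyses, and Section 13 leaves the detail to a later SAP.

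**The concern.** The study has one arm and one assigned dose, so any evidence that tumor shrinkage depends on exposure must come from differences in concentration between patients. With 50 patients and 15 responders expected at the design ORR (50 × 0.30), two halves by blood level hold 25 patients and about 7 or 8 responders each. Grouping discards the ordering of exposure within each half. Using response discards how far each tumor shrank or grew. The resulting tables could show no clear pattern in data that do contain one, and what they show would depend on cut points not yet chosen. This point concerns the blood-level half of the subgroup sentence, not the treatment-duration half.

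**Working it through.** **The plan's own figure.** There is none for exposure-response: no test, effect size or power target is stated.

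**Inputs from the documents.** n = 50 and alternative ORR = 30% (Section 13.1).

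**Assumptions not in the documents.** Exposure and tumor shrinkage are bivariate normal with correlation rho of 0.3, 0.4 or 0.5. A response is the top 30% of shrinkage. Subgroups are a median split, with three and four groups as variants. A two-sided 5% test serves only as a yardstick of information. All 50 patients have usable concentrations and scans.

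**Analytic check at rho = 0.4.**
- Both continuous, by Fisher's z: power = Φ(atanh(rho) × √(n − 3) − 1.96) = Φ(0.4236 × √47 − 1.96) = Φ(0.944) = 0.83.
- Median split against response: the model gives an ORR of 41.3% in the upper half and 18.7% in the lower, a difference of 0.226. The null standard error is √(2 × 0.30 × 0.70 / 25) = 0.1296. The alternative standard error is √((0.413 × 0.587 + 0.187 × 0.813) / 25) = 0.1256. Power = Φ((0.226 − 1.96 × 0.1296) / 0.1256) = Φ(−0.22) = 0.41.
- The same arithmetic in descriptive terms: the 95% half-width for the difference between halves is 1.96 × 0.1256 = 0.246, which is larger than the expected difference of 0.226.

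**Simulation** (n = 50, ORR 30%; 10,000 trials per setting, 4,000 for the Spearman and three- or four-group rows). Rejection rates:

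| Analysis | rho 0.3 | rho 0.4 | rho 0.5 |
|---|---|---|---|
| Continuous exposure, percent change (Pearson) | 56.5% | 83.3% | 96.5% |
| Continuous exposure, percent change (Spearman) | 51% | 78% | 94% |
| Median split, percent change | 38.6% | 63.2% | 84.3% |
| Continuous exposure, yes/no response | 35.2% | 58.4% | 80.3% |
| Median split, yes/no response (chi-square) | 26.0% | 42.3% | 61.3% |
| Median split, yes/no response (Fisher) | 15.8% | 29.4% | 47.2% |
| Three groups, yes/no response (chi-square) | 21.3% | 38.8% | 58.9% |
| Four groups, yes/no response (chi-square) | 20.3% | 35.3% | 54.2% |

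**Splitting the loss at rho = 0.4 (Pearson and chi-square).** Replacing percent change by response costs 83.3 − 58.4 = 24.9 points. Then grouping exposure costs 58.4 − 42.3 = 16.1 points. Together that is 41.0. The split depends on the order: grouping exposure first costs 83.3 − 63.2 = 20.1 points, and cutting the outcome then costs 63.2 − 42.3 = 20.9.

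**Fewer evaluable patients.** At n = 40 and rho = 0.4 the rates are 74.4% for both continuous (Pearson) and 34.6% for the median split with response (chi-square).

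**The case against.** A reader might infer that the plan compares a yes/no response across blood-level groups and so forfeits about 40 points of power. The documents do not support that reading, for four reasons.

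- Section 13.3 rules out inferential analysis and Section 13.3.4 speaks of summaries, so there is no test with power to lose.
- The outcome is not only yes/no. Best confirmed response has several categories, and PFS, DOR and TTR are also summarized in each subgroup. DOR and TTR do, however, cover responders only.
- The 41 points add two separate choices. The quoted sentence concerns grouping exposure, which accounts for about 16 of them once response is the outcome.
- The correlation, the normal model, the cuts and the test are all assumptions. The model also favors percent change, because it makes response an exact threshold of it. Actual ORR needs confirmation and IRC assessment, and it takes account of new and non-target lesions.

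It is also fair that exposure-response is not a stated objective, that the listings and individual concentration figures leave a later analysis possible, and that the later SAP could add one. Nor would a true association usually be missed at every strength: at rho = 0.5 the median split detects it 61% of the time.

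These points limit the claim but do not remove it. A descriptive contrast between two groups of 25 is imprecise whether or not it is tested. Section 13.3.5 already plans exploratory regression for biomarkers, so modeling exposure would fit the plan. The protocol text names subgrouping as the method, and it is better to settle the alternative before results are seen.

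**Conclusion.** The point holds as a cheap improvement to an exploratory analysis. It is not an error in the primary analysis. In the text available, efficacy is linked to PT2385 concentration only by descriptive subgroups with unstated cuts, and percent tumor change is displayed but never related to exposure.

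The cost is information. Under the stated model at rho = 0.4, the detection rate is 42% with both variables cut, 58% with exposure kept continuous, and 78% (Spearman) to 83% (Pearson) with both continuous. The direction is the same at every setting shown. The size rests on assumptions outside the documents and should be quoted as a range, not as a property of the plan.

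**What to change.** In Section 13.3.4 and the synopsis, add a main exploratory exposure-response analysis:

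1. **Exposure:** mean log pre-dose PT2385 concentration over whichever of the Week 3, 5 and 9 samples are available, kept continuous. These samples precede the first scheduled scan. Exclude and count patients who lack all three.
2. **Percent change in ccRCC tumor burden, growth included:** Spearman correlation and a linear slope with 95% CI. Use the change at a fixed scan (for example Week 13 or Week 25) beside the maximum, because the maximum depends on how many scans a patient has.
3. **Confirmed response by logistic regression and PFS by Cox regression,** on the same continuous exposure.
4. **Section 13.3:** amend the statement on inferential analyses so that these exploratory estimates and intervals are allowed and labelled as such.
5. **Subgroup tables:** keep them as supporting displays, with the cuts and the definition of blood level fixed in advance.

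Adding percent change as an outcome for the baseline biomarkers in Section 13.3.5 is optional, since regression is already planned there.

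The cost is protocol and SAP wording and a little programming, with no new data, visits or patients. There are limits: the slope assumes a roughly linear relation and Spearman a monotone one, percent change ignores new and non-target lesions (hence the response model beside it), and exposure after Week 9 is not used.

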7.2.1. Patient Inclusion Criteria

Patients must meet all of the following criteria to be enrolled in this study.

- 1. Has the ability to understand and willingness to sign a written informed consent form before the performance of any study procedures
- 2. Is of age ≥ 18 years
- 3. Has at least 1 measurable ccRCC tumor and no solid ccRCC tumor > 3.0 cm, based on radiologic diagnosis (histologic diagnosis not required); may have VHL disease-associated lesions in other organ systems
- 4. Has a diagnosis of von Hippel-Lindau disease, based on a germline VHL alteration
- 5. Has an Eastern Cooperative Oncology Group (ECOG) performance status of 0 to 2 (see Appendix 2)
- 6. Has normal organ and marrow function as defined below:
 - White blood cell count $\geq 3,000/\mu L$, absolute neutrophil count $\geq 1,500/\mu L$, hemoglobin level ≥ 9 g/dL without transfusion support within 2 weeks prior to enrollment; platelet count $\geq 100,000/\mu L$;
 - Serum creatinine level $\leq 2.0 \times$ ULN or measured 24-hour creatinine clearance ≥ 30 mL/min; and
 - Levels of AST and ALT < $2.5 \times$ ULN, total bilirubin < $1.5 \times$ ULN (< $3 \times$ ULN in patients with Gilbert's disease), and alkaline phosphatase $\leq 2.5 \times$ ULN

- 7. If a female patient of child-bearing potential, or a male patient with a female partner of child-bearing potential (defined as all women physiologically capable of becoming pregnant), must agree to use highly effective methods of contraception during screening, during the period of drug administration and for 30 days after stopping study drug administration. Highly effective contraception methods include the following:
 - Total abstinence,
 - Male or female sterilization, or
 - Combination of any 2 of the following (a + b or a + c or b + c):
 - a. Use of oral, injected or implanted hormonal methods of contraception
 - b. Placement of an intrauterine device (IUD) or intrauterine system (IUS)
 - c. Barrier methods of contraception: condom or occlusive cap (diaphragm or cervical/vault caps) with spermicidal foam/gel/film/cream/vaginal suppository
- 8. If a female patient of child-bearing potential, must have a negative serum pregnancy test result within 7 days before first administration of study drug.

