10. ASSESSMENT OF EFFICACY

10.1. Efficacy Parameters

Primary endpoint: Best confirmed response in VHL disease-associated ccRCC tumors, defined as the proportion of the best confirmed response of CR or PR (as assessed by the Independent Review Committee (IRC)) as determined by RECIST 1.1, modified to follow ccRCC tumors only. ORR is defined as the proportion of patients with a best confirmed response of CR or PR.

Secondary endpoints:

- Progression-free survival (PFS) in VHL disease-associated ccRCC tumors, defined as the interval from the start of study treatment until the earlier of the first documentation of disease progression determined by RECIST 1.1 or death from any cause, and calculated for patients with a best confirmed response of CR or PR
- Duration of response (DOR) in VHL disease-associated ccRCC tumors, defined as the interval from the first documentation of response, as determined by RECIST 1.1, to the earlier of the first documentation of disease progression or death from any cause, and calculated for the patients with a best confirmed response of CR or PR
- Time to response (TTR) in VHL disease-associated ccRCC tumors, defined as the interval from the start of study treatment to the first documentation of a response, as determined by RECIST 1.1, and calculated for patients with a best confirmed response of CR or PR
- Best confirmed response, PFS, DOR, and TTR for non-ccRCC tumors associated with VHL disease in different organ systems, by modifying RECIST 1.1 criteria to assess tumors in individual organ systems (Appendix 4)

Exploratory endpoint:

• Changes in PD markers (e.g., serum EPO)

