13.2. Analysis Populations

The analysis populations include the following:

Enrolled Population: The Enrolled Population is defined as all patients who have been screened and have provided written informed consent. This population will be used for the summary of patient disposition and data listings.

Efficacy Analysis Set: The Efficacy Analysis Set is defined as all patients who have been enrolled and received at least 1 dose of PT2385. This population is the primary population for analysis of efficacy.

Safety Analysis Set: The Safety Analysis Set is defined as all patients who have been enrolled and received at least 1 dose of PT2385. This population is the primary population for the summaries of demographics, baseline data, safety data, and exposure.

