Appendix 3 RECIST 1.1 Summary

Abstracted from Eisenhauer EA, et al. 2009

Time Point Response: Patients with Target (± Non-Target) Disease

Target lesions	Non-target lesions	New lesions	Overall response
CR	CR	No	CR
CR	Non-CR/non-PD	No	PR
CR	Not evaluated	No	PR
PR	Non-PD or not all evaluated	No	PR
SD	Non-PD or not all evaluated	No	SD
Not all evaluated	Non-PD	No	NE
PD	Any	Yes or No	PD
Any	PD	Yes or No	PD
Any	Any	Yes	PD

CR = complete response, PR = partial response, SD = stable disease, PD = progressive disease, and NE = not evaluable

Time Point Response: Patients with Non-Target Disease Only

Non-target lesions	New lesions	Overall response
CR	No	CR
Non-CR/non-PD	No	Non-CR/non-PD
Not all evaluated	No	NE
Unequivocal PD	Yes or No	PD
Any	Yes	PD

CR = complete response, PD = progressive disease and NE = not evaluable

A 'Non-CR/non-PD is preferred over 'stable disease' for non-target disease since SD is increasingly used as an endpoint for assessment of efficacy in some trials so to assign this category when no lesions can be measured is not advised.

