Appendix 4 Evaluation of Non-Renal VHL Related Disease

Wherever possible, non-renal lesions will be assessed using RECIST 1.1, modified to assess that type of lesion only. Assessments of specific lesion types will be made as described below.

• Pancreatic Lesions

CT/MRI of the pancreas will be obtained at baseline and follow-up and evaluated using RECIST 1.1.

• Pheochromocytomas

Serum and urine catecholamine levels will be evaluated at baseline and follow-up visits.

Adrenal Lesions

CT/MRI of the adrenal glands will be obtained at baseline and follow-up and evaluated using RECIST 1.1

• CNS Hemangioblastomas

MRI of the brain and spine will be obtained at baseline and follow-up and evaluated using RECIST 1.1

• Retinal Angiomas

Evaluation of these lesions at baseline and follow-up will include the following:

- o Fundoscopic examination with notation of the size and location of angiomas
- Visual acuity and visual fields in patients with lesions close to the macula or affecting vision.
- Inner Ear Endolymphatic Sac Tumors

CT/MRI of the head will be obtained at baseline and follow-up and evaluated using RECIST 1.1.

• Epididymal Cystadenomas

The epidydimis will be assessed at baseline and follow-up using ultrasound.

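### Each non-ccRCC ORR counts every patient with that tumor type, although patients with no measurable lesion in the organ cannot score a PR; the rate is diluted by an unknown, possibly zero, amount

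*Combined protocol and SAP*

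**What the plan says.** Section 13.3.4 plans ORR, PFS, best confirmed response, DOR and TTR for the non-ccRCC tumors, "based on the subgroups of patients in the Efficacy Analysis Set who have the particular type of tumor". Section 13.2 adds no measurability condition: "The Efficacy Analysis Set is defined as all patients who have been enrolled and received at least 1 dose of PT2385".

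The entry criteria in Section 7.2.1 treat the two kinds of disease differently. For the kidney, the patient "Has at least 1 measurable ccRCC tumor and no solid ccRCC tumor > 3.0 cm". For other organs, the patient "may have VHL disease-associated lesions in other organ systems", with no size or measurability requirement.

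Appendix 4 says that, where possible, "non-renal lesions will be assessed using RECIST 1.1, modified to assess that type of lesion only". It names RECIST 1.1 for pancreatic lesions, adrenal lesions, CNS hemangioblastomas and endolymphatic sac tumors. The statistical methods in the Synopsis describe the same modification, namely that organ systems are judged separately. Neither place changes the response categories or sets a rule for non-measurable lesions.

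Appendix 3 has two time-point tables. The second, "Time Point Response: Patients with Non-Target Disease Only", allows CR, Non-CR/non-PD, NE and progressive disease. Its footnote explains why stable disease is not used there: "to assign this category when no lesions can be measured is not advised".

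Section 10.1 defines the rate: "ORR is defined as the proportion of patients with a best confirmed response of CR or PR". Section 10.1.1.1 plans an ORR for each of the other VHL tumor types.

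**The concern.** Read together, these rules put some patients in an organ's denominator with only one route into the numerator. If all of a patient's lesions in the organ are non-measurable, even marked shrinkage is recorded as Non-CR/non-PD. Only disappearance of every lesion counts as a response.

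The organ-level ORR then depends on two things: how well the drug works there, and how many patients happened to have a measurable lesion there. Two organs with the same drug effect could show different rates, and a reader who sets them side by side, or against the ccRCC rate, could be misled. The effect on non-ccRCC tumors is a named secondary objective (Section 5.2), so these rates will be read.

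**Working it through.** The documents state no rate, sample size or power for any non-ccRCC ORR, so there is no planned figure to reproduce. The check is whether the rules combine as described, and what follows if they do.

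**Rules, in order**
1. Denominator: all treated patients with the tumor type (Sections 13.3.4 and 13.2).
2. Measurability at entry: guaranteed by the criteria for ccRCC only (Section 7.2.1).
3. Organ-level scoring: RECIST 1.1 applied to one lesion type at a time (Appendix 4; Synopsis).
4. Categories without a target lesion: CR, Non-CR/non-PD, NE, progressive disease; no PR (Appendix 3).
5. Numerator: best confirmed CR or PR (Section 10.1).

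**Formula**
- f = share of patients with the tumor type who have no measurable lesion in that organ
- p = CR + PR rate in patients with a measurable lesion
- c = CR rate in patients with non-measurable lesions only

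Expected reported ORR = (1-f)p + fc. Shortfall against p = p - [(1-f)p + fc] = f(p-c). It is positive when f > 0 and c < p, and zero when f = 0.

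**Illustration.** None of f, p and c is in the documents, so all values are assumptions. The 30% is the ccRCC alternative from Section 13.1, borrowed only as an example.

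| f | ORR, p = 30%, c = 0 | Shortfall | ORR, p = 30%, c = 10% | Shortfall |
|---|---|---|---|---|
| 0 | 30% | 0 points | 30% | 0 points |
| 20% | 0.8 × 30 = 24% | 6 | 24 + 0.2 × 10 = 26% | 4 |
| 40% | 0.6 × 30 = 18% | 12 | 18 + 0.4 × 10 = 22% | 8 |
| 60% | 0.4 × 30 = 12% | 18 | 12 + 0.6 × 10 = 18% | 12 |

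Raising c from 0 to 10% cuts the shortfall by a third, because p - c falls from 30 to 20 points.

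**What the change does to precision.** Assume 20 patients have the tumor type, 14 of them with a measurable lesion, and 6 respond, all among the 14. The planned rate is 6/20 = 30.0% (exact 95% CI 11.9 to 54.3). The rate in patients with a measurable lesion is 6/14 = 42.9% (17.7 to 71.1). The interval widens from 42.4 to 53.4 points.

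**The case against.** The strongest reply is that nothing is misestimated. A response rate among all treated patients with, say, a pancreatic lesion is a legitimate and conservative quantity, in line with the Efficacy Analysis Set. That stands: the rate is low only relative to the rate in patients with a measurable lesion. A reader might infer that the planned ORR is simply biased downward, or by a known amount. The documents do not support that, because f may be zero in any organ and patients with non-measurable lesions can still score a CR.

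The plan also summarizes best confirmed response for each tumor type, where Non-CR/non-PD would stand apart from stable disease if it is tabulated. This helps in part. It would not separate the CR, progressive disease and NE cases by measurability, and it would not change the ORR.

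That the non-target-only table governs each organ is an inference; no section says so outright. It is the natural reading, since the only stated change to RECIST is to look at one organ or lesion type at a time, but it remains an assumption.

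The consequence is limited. Section 13.3 rules out inferential analyses, no threshold is attached to any non-ccRCC ORR, and no comparison between organs is planned. The introduction to Section 13 leaves detail to a formal SAP before database lock, where the denominator could be refined. The text at hand, however, states a denominator, and it has no measurability rule.

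A reader might also take the ccRCC ORR as a fully measurable benchmark. Section 7.2.1 does not say who judges measurability at entry, while the primary ORR uses the IRC read (Section 13.3.4), so a measurable ccRCC tumor on the IRC's own read is not guaranteed for every patient.

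**Conclusion.** The point holds in a limited form. Followed as written, Section 13.3.4 dilutes each imaged non-ccRCC ORR by f(p-c) relative to the rate in patients with a measurable lesion. The direction follows from the rules if c is below p and the non-target-only table applies organ by organ. The size cannot be computed from the documents: with p = 30% it runs from 0 to 18 points over the assumed values above.

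It would be wrong to extend this to the primary analysis. The ccRCC ORR, the Stage 2 decision and the 13-of-50 rule do not use the non-ccRCC rates. Nor does it carry over directly to pheochromocytomas, retinal angiomas or epididymal cystadenomas. For these, Appendix 4 lists catecholamines, funduscopy and visual tests, and ultrasound, without a rule for turning them into CR or PR; that is a separate gap.

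The change is worth making because it is cheap and makes a secondary result interpretable. It does not repair an invalid analysis.

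**What to change.** In Section 13.3.4, and in the formal SAP:

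- Define the main ORR denominator for each imaged non-ccRCC tumor type as patients with at least 1 measurable lesion of that type at baseline, as judged by the assessor whose response read is being summarized (investigator or IRC).
- Tabulate patients with only non-measurable lesions of that type separately, as CR, Non-CR/non-PD, progressive disease or NE.
- Keep the rate over all patients with the tumor type as a supplementary figure, so nothing planned is lost.
- Organ-level PFS may keep both groups, since progression can be scored in either table.

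Waterfall plots need no change, as they are planned for ccRCC only.

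The cost is some wording, additional table rows, and a record of baseline measurability by organ for each assessor, which the documents do not currently describe for non-renal lesions. The downsides are smaller denominators, wider intervals, and possibly different denominators for the investigator and IRC reads.
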